Anesthesia. Sedation will be achieved by target-controlled IV infusion of propofol (see **Appendix I** below for detailed plan). The IV line will be placed after application of a local anesthetic. Propofol will be administered by intravenous infusion. Nasal cannula will be used for supplemental O₂ and CO₂ sampling. All anesthesia equipment, supplies, and drugs will be provided by anesthesiologists from the University of Michigan Health System. We will manually control the infusion of propofol to achieve target effect-site concentrations of 1.5, 2.0, 2.5, and 3.0 µg/ml in a stepwise fashion. Each target concentrations will be maintained for 4 minutes. In this way, we will be able to titrate the anesthetic level using those dose increments to reach the point of loss of behavioral responsiveness (LOR). In order to minimize head motion-related artifacts, the effect-site concentration will be maintained at one step above the expected concentration for LOR for approximately 32 minutes. For example, if a participant loses responsiveness at 2.5 µg/ml, we will maintain 3.0 µg/ml effect-site concentration during the entire LOR period (Fig. 2). For exceptional cases when participants retain responsiveness at 3.0 µg/ml (occurrence rate of ~5.6% in our previous studies), we will increase target effect-site concentrations to 3.5 µg/ml (assuring LOR in 99.5% population) and maintain at maximum of 4.0 µg/ml. After that, the infusion will be terminated and the propofol concentration is allowed to gradually decrease. Participants will be instructed to perform a behavioral test, taking a rest, or listen to the music as described below.

[figure not shown]

Fig. 2. Experimental design for fMRI. Figure shows hypothetical case in which the participant loses responsiveness (LOR) at propofol effect-site concentration (ESC) of 2.5 µg/ml.

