Primary outcome measure: Blood Oxygen Level Dependent (BOLD) Response to sensory stimuli during sedation (timeframe: baseline to 90 minutes).

Secondary outcome measure: Squeeze Pressure, defined as measurement of force of participants' hand squeezing on a rubber ball in response to instructions (timeframe: baseline to 90 minutes).

Data Analysis

Image analysis will be conducted using AFNI (<http://afni.nimh.nih.gov/afni>). 1) The first two frames of each fMRI run will be discarded; 2) Slice timing correction; 3) Rigid head motion correction/realignment within and across runs; frame-wise displacement (FD) of head motion will be calculated using frame-wise Euclidean Norm (square root of the sum squares) of the six-dimension motion derivatives. A frame and its each previous frame will be tagged as zeros (ones, otherwise) if the given frame's derivative value has a Euclidean Norm above FD=0.5 mm; 4) Coregistration with high-resolution anatomical images; 5) Spatial normalization into Talairach stereotactic space; 6) Using AFNI's function 3dTproject, the time-censored data will be high-pass filtered above 0.008 Hz. At the same time, various undesired components (e.g., physiological estimates, motion parameters) will be removed via linear regression. The undesired components include linear and nonlinear drift, time series of head motion and its temporal derivative, binarized FD time series (output data included zero values at censored time points), and mean time series from the white matter and cerebrospinal fluid; 7) Spatial smoothing with 6 mm full-width at half-maximum isotropic Gaussian kernel; 8) The time-course per voxel of each run will be normalized to zero mean and unit variance, accounting for differences in variance of non-neural origin (e.g., distance from head coil).

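### Mean Frequency is summed up to 0.625 Hz over series with zeroed frames, and nothing in its analysis separates a between-state difference in residual noise or censoring from a change in timescale

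*Combined protocol and SAP*

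**What the plan says.** All references are to the combined protocol and SAP.

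- **Filter (Data Analysis, step 6).** "the time-censored data will be high-pass filtered above 0.008 Hz". No low-pass limit is stated here or elsewhere.
- **Censoring (steps 3 and 6).** When head motion exceeds 0.5 mm, "A frame and its each previous frame will be tagged as zeros (ones, otherwise"). The regressors in step 6 include the "binarized FD time series (output data included zero values at censored time points"). No interpolation or gap-tolerant spectral method is described.
- **Noise control before MF.** In step 6, "various undesired components (e.g., physiological estimates, motion parameters) will be removed via linear regression"; the list covers drift, motion and its derivative, and white-matter and CSF means. Step 7 is "Spatial smoothing with 6 mm full-width at half-maximum isotropic Gaussian kernel". Participants are told to keep still (fMRI Protocol). For the LOR scans the Anesthesia section adds: "In order to minimize head motion-related artifacts, the effect-site concentration will be maintained at one step above the expected concentration for LOR".
- **Scaling (step 8).** "The time-course per voxel of each run will be normalized to zero mean and unit variance".
- **MF (Data Analysis, intrinsic TRWs).** A Hamming-tapered periodogram is computed for each resting-state voxel series. MF is the power-weighted mean frequency over all bins, and a lower MF is taken to mean slower dynamics. No between-state test for MF is named; the phase-randomization test is described for inter-subject correlation only.
- **Role of MF.** The listed outcomes are BOLD response and squeeze pressure. MF is the only index given for the hypothesis, in Rationale and Hypothesis and in Anticipated Results, that sedation prolongs intrinsic timescales.

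**The concern.** MF is a ratio of sums over the whole spectrum. About 85% of the retained band lies above 0.1 Hz, so a modest amount of broadband residual noise carries a lot of weight. Zeros left at censored frames also spread low-frequency power upwards. If noise share and censored fraction are equal in all states, the contrast between states is only diluted. If they differ, MF can fall with no slowing, or fail to fall despite real slowing.

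The upstream steps lower the noise but do not make what remains equal across states. Unit-variance scaling cannot help, because scale cancels in MF. The Hamming taper addresses finite-sample spectral bias, not noise share or gaps. What is at stake is how a lower MF under LOR may be read. Anticipated Results also proposes to correlate the degree of prolongation with the spatial extent of inter-subject correlation.

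**Working it through.** **Inputs from the documents.** TR = 0.8 s; runs of 16 min; two frames dropped; high-pass at 0.008 Hz.

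- Highest frequency: 1/(2 × 0.8) = 0.625 Hz.
- Frames: 960/0.8 = 1200, less 2 = 1198.
- Share of the band above 0.1 Hz: (0.625 − 0.1)/(0.625 − 0.008) = 0.85.
- Five per cent censored: about 60 frames, or 30 separate frame pairs.

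**Assumptions, not in the documents.** The signal spectrum is 1/f from 0.008 Hz up to 0.1, 0.2 or 0.625 Hz. Residual noise is white, at 6, 15, 30 or 50% of power where MF is computed. Slowing is a change of spectral exponent from 1.0 to 1.5. The noise range is wide because the effect of smoothing depends on the grid. A 50% share falls to 6.2% if noise is independent on the 3.4 × 3.4 × 4 mm acquisition grid, but realignment and "Spatial normalization into Talairach stereotactic space" resample first, and the output grid is not stated.

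**Analytic check, signal to 0.1 Hz.** Mean frequency of the signal: (0.1 − 0.008)/ln(0.1/0.008) = 0.0364 Hz. Of white noise: (0.008 + 0.625)/2 = 0.3165 Hz. For noise share h, MF = (1 − h) × 0.0364 + h × 0.3165.

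- h = 0.06: MF = 0.0532 Hz.
- Noise 10% higher relative to signal: h = 0.066/(0.94 + 0.066) = 0.0656, MF = 0.0548, or +2.9%.
- Five more percentage points, h = 0.11: MF rises by 0.05 × 0.2801 = 0.0140, or +26%.

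That last step is not small. Noise relative to signal goes from 0.06/0.94 to 0.11/0.89, a factor of 1.94. From 15, 30 and 50% the same five points are factors of 1.42, 1.26 and 1.22.

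**Simulation.** 1,500 series of 1198 frames, Hamming taper. Change in broadband MF (%) at noise shares of 6 / 15 / 30 / 50%:

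| Change between states | Signal to 0.1 Hz | Signal to 0.2 Hz | Signal to 0.625 Hz |
|---|---|---|---|
| Noise 10% higher relative to signal | +3.0 / +4.5 / +4.8 / +3.8 | +1.9 / +3.3 / +3.8 / +3.3 | +0.6 / +1.3 / +1.8 / +1.8 |
| Noise share +5 points | +26.6 / +17.8 / +11.5 / +7.8 | +17.2 / +13.1 / +9.3 / +6.8 | +5.7 / +5.2 / +4.5 / +3.8 |
| 5% censored, scattered pairs | +13.8 / +8.4 / +4.5 / +2.1 | +8.7 / +6.0 / +3.5 / +1.8 | +2.9 / +2.4 / +1.7 / +1.0 |
| Slowing only | −13.2 / −7.6 / −3.8 / −1.8 | −23.6 / −15.9 / −9.2 / −4.7 | −43.1 / −35.1 / −24.8 / −15.0 |
| Slowing and noise +5 points | +14.5 / +10.9 / +8.0 / +6.2 | −4.9 / −1.8 / +0.9 / +2.5 | −34.9 / −27.8 / −18.6 / −9.7 |

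One point of censoring, or five points in bursts of 8 to 15 frames, gives at most about +5%.

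**Same cases in a 0.008–0.1 Hz band.** Five points of white noise or 5% zeroed frames move MF by at most about 1.5%. Slowing shows as −17 to −21%.

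**Where the band does not help.** Five points of residual noise at 0.008–0.03 Hz lower in-band MF by about 2.5 to 6.5%. Five points at 0.05–0.1 Hz raise it by about 5 to 11%.

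**The case against.** The strongest reply is about size. Each participant is scanned in all states in one session on one scanner, so scanner noise has no obvious reason to change; a physiological or signal-amplitude change would have to do it. The largest table entries need noise relative to signal nearly to double, and the large censoring effects need some 30 more separate movements in one resting run than in another. This stands, and it is why the 10% row is the better guide.

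Three further points also stand. The plan cites an earlier study (reference 8) for MF as a timescale index, and that source may set a frequency range; it was not available here, so the statement is only that this document sets none. The low-pass account in Rationale and Hypothesis predicts lost fast power, so a cap could hide part of a real effect. And a band limit gives no protection against noise inside the band.

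A reader might infer that the predicted fall in MF under LOR would be an artefact, because the Anesthesia section aims to reduce motion in those scans. Less noise or censoring under LOR would indeed lower MF. But the section states an aim, not achieved motion or residual noise by state, so the direction is not established. Nor do the documents support saying that noise is left uncontrolled: several steps reduce it.

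**Conclusion.** The concern holds in a conditional form. As written, MF runs to 0.625 Hz on series with zeros at censored frames, and a lower value is read as a longer timescale with no step to exclude a between-state difference in residual broadband noise or censoring.

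Under the stated assumptions, a 10% relative rise in white noise moves MF by about 3 to 5%, 2 to 4% or 1 to 2%, for signal reaching 0.1, 0.2 or 0.625 Hz. Five points of noise give +27 to +8%, +17 to +7% or +6 to +4%, the upper ends only with a near-doubling of noise relative to signal. Censoring matters only with many scattered movements. If signal reaches 0.625 Hz, the artefact is small against the assumed slowing.

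A reader might take the 27% figure as the expected bias, or turn it into a false-claim rate. Neither follows: the documents give no noise share, no censoring rate by state and no between-subject SD of MF. Because MF is not a listed outcome, this is a worthwhile, inexpensive improvement and not a flaw in the trial's primary result.

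**What to change.** Keep broadband MF and add to Data Analysis:

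> MF will also be computed over a fixed band whose upper limit is set and justified before analysis (for example 0.008–0.1 Hz), compared between states with the same test and at the same level (voxel, region or global) as broadband MF, and reported with estimates and confidence intervals. Censored fraction and share of power above the band will be tabulated for wakefulness, LOR and ROR. A prolonged timescale will be claimed without qualification only if the in-band estimate also falls. A change seen only in broadband MF will be reported as possibly due to noise, censoring or loss of fast signal.

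The 0.1 Hz limit is illustrative and not from the documents; the investigators should choose and justify their own. The between-state test and level for MF also have to be named, since the plan gives neither.

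**Cost.** One further sum per voxel and one table, with no new data and no change to preprocessing.

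**Limits to state in the plan.** Low-frequency residual noise at 0.008–0.03 Hz lowers both versions of MF together, so agreement between them does not exclude it. A genuine loss of fast power may appear only in broadband MF, and the power-share table alone cannot tell fast signal from noise. The in-band effect can also be about half the broadband one: −21% against −43% with signal to 0.625 Hz and 6% noise.

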1) SPGR high-resolution images. T1 weighted spoiled gradient recalled echo (SPGR) images will be acquired for high spatial resolution of anatomical images with parameters: 170 sagittal slices, 1.0mm thickness (no gap), TR=8.1s, TE=3.7ms, flip angle=8°, FOV=24cm, image matrix 256×256.

2) Functional MRI images. A gradient-echo EPI pulse sequence will be employed to acquire functional images over the whole brain with parameters: 28 slices, TR/TE=800/25ms (multiband fMRI acquisition), slice thickness=4mm, in-plane resolution=3.4×3.4mm; MB factor=4; field of view (FOV)=220mm, flip angle=76°, image matrix: 64×64. Verbal instructions were presented through earphones. Eight fMRI scans (16-min per scan) will be conducted throughout the experiment. The eight scans will include 16-min resting-state and 16-min music-listening during wakefulness baseline; 16-min behavioral test during propofol induction; 16-min resting-state and 16-min music-listening after loss of behavioral responsiveness; 16-min behavioral test during emergence period (after propofol infusion is terminated); 16-min resting-state and 16-min music-listening after recovery of behavioral responsiveness. There will be a 1-5 minute break in between scans. The imaging protocols and data acquisition will be completed within 2.5 hours scanning session for each subject.

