The music evoked activity, will be quantified by inter-subject correlation (inter-SC) of the fMRI responses (7), depends systematically on the music structure coherence. For instance, early auditory areas respond reliably to low-level acoustic features of music, whereas frontal areas process long-timescale musical structures, on the order of minutes. This analysis provides a measure of the reliability of the responses through the functional hierarchy by comparing the BOLD response time courses across different subjects. The inter-SC analysis will be performed on a voxel-by-voxel basis. First, the Pearson product-moment correlation will be computed between a voxel's fMRI time course in one individual and the average of that voxel's fMRI time courses in the remaining subjects. Next, the average correlation coefficient will be calculated at every voxel. Finally, it will produce an average inter-SC map during music presentation period. Statistical significance of inter-SC for each state (i.e. wakefulness baseline, LOR period, and ROR period) and the difference between states (e.g. wakefulness baseline vs. LOR period) will be assessed using a phase-randomization procedure (forming a null distribution).

Intrinsic TRWs will be calculated from the resting-state data. We will use Mean Frequency (MF) of fMRI signal fluctuations to index the TRW length (8). Specifically, power spectrum will be obtained by computing the periodogram of each voxel time series using AFNI program 3dPeriodogram. Tapering was applied using the Hamming window to reduce bias and error variance for spectral estimation in finite data (9). The MF of a spectrum will be calculated as the sum of the product of the spectrogram power intensity and the frequency, divided by the total sum of spectrogram power intensity:

$$MF = \frac{\sum_{i=0}^n P_i F_i}{\sum_{i=0}^n P_i}$$

where n is the number of frequency bins in the spectrum, F_i is the frequency of spectrum at bin i of n, and P_i is the power intensity of spectrum at bin i of n. Lower MF indicates a shift toward a longer timescale or slower dynamics.

Anticipated Results and Implications

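### Motion-censored frames stay as zeros in the series that inter-SC correlates, so inter-SC falls as the censored fraction rises, and the wakefulness–LOR contrast depends on motion in each state

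*Combined protocol and SAP*

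**What the plan says.** All of the relevant text is in the Data Analysis section, apart from the acquisition figures.

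- **Tagging (step 3).** When the motion derivative exceeds 0.5 mm, "A frame and its each previous frame will be tagged as zeros (ones, otherwise").
- **Output of censoring (step 6).** The censored points are not removed. The list of regressed components ends with "binarized FD time series (output data included zero values at censored time points").
- **Scaling (step 8).** "The time-course per voxel of each run will be normalized to zero mean and unit variance". No frames are excluded from this step.
- **Inter-SC.** The correlation is taken "between a voxel's fMRI time course in one individual and the average of that voxel's fMRI time courses in the remaining subjects". Nothing restricts it to retained frames.
- **Inference.** Each state is tested, and "the difference between states (e.g. wakefulness baseline vs. LOR period) will be assessed using a phase-randomization procedure".

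Step 7 smooths in space only, so a frame that is zero in every voxel is still zero afterwards. The plan sets no minimum number of retained frames and does not compare or match censoring between states. Its only state-specific measure against motion is in the Anesthesia paragraph and Appendix I, where the LOR maintenance level is chosen partly to limit motion artifact.

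**The concern.** Drift removal centers the retained data near zero, so a zero left at a censored frame acts as an observation equal to the mean. It adds nothing to the covariance with other participants, but the frame still counts in the series. When participants move at different moments, one participant's zero is paired with another's real signal, and the correlation is diluted.

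Inter-SC is how the plan quantifies music-evoked activity, and the expected finding is lower inter-SC during LOR. If states differ in censored fraction, part of any difference in inter-SC reflects motion. The phase-randomized null does not correct this. It breaks shared timing, so it describes what happens with no common response. It does not describe an equal response with unequal censoring.

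**Working it through.** **Inputs from the documents**

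- Run length: "Eight fMRI scans (16-min per scan) will be conducted throughout the experiment".
- Repetition time: "TR/TE=800/25ms (multiband fMRI acquisition").
- Frames: 16 × 60 / 0.8 = 1200 per run, less the two discarded, gives 1198.
- Group size: N = 25 (recruitment section).

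The plan states no inter-SC value, censored fraction or expected bias, so there is no figure of its own to reproduce.

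**Assumptions**

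- Pairwise correlation ρ between participants: 0.15 as the main case, with a range of 0.02 to 0.3.
- Censored fraction c: 2% to 30%.
- Censoring times are independent across participants.

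**Formula**

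With zero-mean series and a fraction c set to zero independently in each participant, the covariance of two participants scales by (1−c)² and each variance by (1−c). The pairwise correlation therefore becomes

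ρ(1−c)² / (1−c) = ρ(1−c).

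The leave-one-out correlation with the mean of the other N−1 participants is

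p·√(N−1) / √(1 + (N−2)p),

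with p = ρ before zero-filling and p = ρ(1−c) after.

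**Numbers at ρ = 0.15**

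- Uncensored: 0.15 × 4.899 / √(1 + 23 × 0.15) = 0.735 / 2.110 = 0.348.
- c = 20%: p = 0.12, and 0.12 × 4.899 / √(1 + 23 × 0.12) = 0.588 / 1.939 = 0.303, a loss of 13%.

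| c | Formula (0.348 uncensored) | Loss | Simulation, zeros kept (0.347 uncensored) | Simulation, retained frames only |
|---|---|---|---|---|
| 2% | 0.344 | 1.2% | 0.341 | 0.345 |
| 5% | 0.338 | 3.1% | 0.338 | 0.347 |
| 10% | 0.326 | 6.3% | 0.324 | 0.342 |
| 20% | 0.303 | 13.0% | 0.306 | 0.344 |
| 30% | 0.278 | 20.1% | 0.275 | 0.331 |

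**Other strengths of response**

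In a separate simulation with autocorrelated signals, the loss at 10% censoring was 9% at ρ = 0.02, 7% at ρ = 0.1 and 6% at ρ = 0.3. At 20% it was 18%, 14% and 12%. The relative loss is larger where the shared response is weaker. Censoring in longer blocks gave nearly the same ratios. When all participants were censored at identical frames there was no loss (ratio about 1.00).

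**Effect on a contrast between states, with the response identical in both (formula, ρ = 0.15)**

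- 2% awake, 5% at LOR: 0.344 against 0.338, an apparent fall of 1.9%.
- 2% awake, 10% at LOR: 0.344 against 0.326, an apparent fall of 5.1%.
- 2% awake, 20% at LOR: 0.344 against 0.303, an apparent fall of 12%.
- 10% awake, 2% at LOR: 0.326 against 0.344, an apparent rise of 5.4% (0.3441 / 0.3264), which would offset a true fall.

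**What remains after the fix**

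With retained frames only, the reference at each frame averages about m = 24(1−c) participants, and inter-SC is about ρ√m / √(1 + (m−1)ρ). At ρ = 0.15 and c = 20%, m = 19.2 and the value is 0.340, a residual loss of 2.3% instead of 13%. In the simulations the residual at 20–30% censoring was about 1–5% at ρ = 0.15, 4–6% at ρ = 0.1 and 1–2% at ρ = 0.3. At ρ = 0.02 it was larger, 8–14%, against 18–28% with zeros kept.

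**The case against.** The strongest objection is about size and direction. The documents report no censored fraction. Participants are told not to move, and the threshold is 0.5 mm of change between frames 0.8 s apart. Nothing shows that 20–30% of frames would be lost, and imbalances of a few percentage points move inter-SC by only a few percent. This stands: the size is conditional and could be small.

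A reader might go further and infer any of the following. The documents do not support them.

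- **That the predicted LOR reduction would be an artifact.** The maintenance level at LOR is chosen partly to limit motion. If that succeeds, wakefulness and recovery are attenuated more, and the fall at LOR is understated.
- **That zero-filling would produce the frontal pattern the plan expects.** The effect is mostly a global scaling. Regions with a weak shared response lose somewhat more, but this is not a selective frontal loss.
- **That any state with more motion must show lower inter-SC.** This needs a true inter-SC above zero and censoring at different times in different participants. The second condition is usual for head motion but is not guaranteed.
- **That individual differences are biased by a known amount.** The calculations vary censoring for the whole group. The only related analysis in the plan is a tentative correlation with the spatial extent of inter-SC, and the effect on it was not calculated.
- **That the plan names inter-SC as its primary outcome.** The named primary outcome is the BOLD response to sensory stimuli during sedation. Inter-SC is the measure that the analysis section uses for music-evoked activity.

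It is also fair to object that dropping frames leaves gaps, whereas phase randomization needs complete, evenly spaced series. The fix has to deal with this.

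**Conclusion.** The concern holds in conditional form. Followed as written, the plan makes inter-SC a function of the censored fraction as well as of the music response. This follows from a stated rule and is not an inference from missing detail. At ρ of about 0.15 with 25 participants, the group loss runs from 1–2% at 2% censoring to about 20% at 30%. What matters for the contrast between states is the difference in censoring, and the documents settle neither its size nor its sign. The figures rest on assumed values of ρ and c and on independent censoring times. The change should be made before analysis, because it is cheap and the bias would otherwise be hard to separate from the effect under study.

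**What to change.** In the Data Analysis section:

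1. Normalize each voxel's series over retained frames only.
2. Compute each participant's correlation over that participant's retained frames. At each frame, build the reference from the other participants retained there.
3. Generate the phase-randomized surrogates on full-length series, stating how gaps are filled for this step alone. Then apply the same participant- and state-specific masks before correlating, so that the null matches the statistic.
4. Report the censored fraction by participant and state.
5. Repeat the contrast between states with censoring matched across states, as a sensitivity check. This addresses the residual loss from having fewer participants in the reference.

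The cost is a small amount of analysis code, with no new data and no added burden on participants. The downsides are series of unequal length, a slightly more complex null, and the residual loss shown above, which is small at moderate ρ but not negligible where the shared response is very weak.

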fMRI Protocol. During the rest-state period, participants will be asked to lay at rest with eyes closed, while trying to stay awake without thinking of anything in particular, and trying not to move. During the music presentation period, participants will be asked to listen to the music, keeping their eyes closed, try not to move, and stay awake. Four types of music, including Jazz, Rock, Pop and Country, will be presented in a pseudo-randomized order. We will select well-known music excerpt and being evaluated by all participants using familiarity and meaningful scales before the experiment. Each piece of music will be edited into 2-min duration. During the behavioral test period, participants will be asked to squeeze an MRI compatible grip dynamometer (a rubber ball) for every 10-second periods (96 cycles in total). The beginning of each cycle will be cued with the spoken word “squeeze”.

The verbal instructions will be programmed using E-Prime 3.0 (Psychology Software Tools, Pittsburgh, PA) and delivered via an audiovisual stimulus presentation system designed for an MRI environment. The volume of the headphones will be adjusted for subject comfort during wakefulness. The volume will be increased to 150% after loss of responsiveness. Behavioral responses will be measured in mmHg of air pressure during squeezing the rubber ball, using BIOPAC (<https://www.biopac.com>) MP160 system with AcqKnowledge software (V5.0). By comparing the timing of “squeeze” instructions (expected motor response) and the actual motor response during and after stepwise propofol infusion, the periods during which a subject loses of responsiveness (LOR), and recovery of responsiveness (ROR) will be determined. The onsets of LOR and ROR were defined at the time of first failure to squeeze, and the first success to squeeze, respectively.

All testing will be performed by the attending anesthesiologists. Spontaneous respiration, end-tidal CO₂, heart rate, and electrocardiogram will be continuously monitored. Noninvasive arterial pressure will be measured with magnetic resonance (MR)-compatible automatic monitor (BIOPAC). Post anesthesia care will consist of checking vital signs for 1 hour by the nursing staff. A wheelchair will be provided to assist the participant if needed. An anesthesiologist will be present during the entire duration of the study.

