We expect to find a spatial hierarchy with reliable responses (inter-SC) to music starting in the primary auditory cortex and adjacent areas of auditory cortex (A1+), processing along the superior temporal sulcus (STS) and further up to the middle and inferior frontal gyrus during conscious wakefulness. We anticipate that during LOR, inter-SC in especially the frontal areas, which process long-timescale musical structures, will be reduced. We also expect to observe that, during

LOR, the intrinsic timescales derived from the resting-state are overall prolonged, and the intrinsic functional gradient of hierarchy is also shrunk. The degree of the intrinsic TRW prolongation and the degree of the functional gradient shrinkage may show a negative correlation with the spatial extension of inter-SC during sedation.

Together, the results should advance our understanding of how the brain processes information at increasing levels of abstraction along the functional hierarchy, and how this information processing may be altered during sedation. The information gained should add further insight into the neural mechanisms for temporal integration in the brain supporting conscious experience of complex stimuli and their degradation under sedation.

Power Analysis

For an fMRI study of cognitive function, Desmond and Glover (10) reported that about 25 subjects are necessary to achieve 80% power for a 0.5% increase of activity. We also conducted power analysis based on our previous study with graded sedation of propofol (11). The average Cohen's d as a measure of the effect size was 0.56. For 80% power and alpha=0.05, N=24 human subjects will be needed. The obtained subject number is also very close to the suggested optimal group size for reliable statistics in functional MRI studies (12). To account for possible failure or attrition, we plan for 30 as the maximum number of subjects.

Biological Variables

We will recruit participants of both sexes with various ethnic/racial backgrounds, aiming for diversity and equal representation. The age range will be limited to 18-40 years in order to limit age-dependent variation in anesthetic requirement for sedation and for participant safety.

Potential Risks

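### The phase-randomization null planned for inter-subject correlation does not fit the wake-versus-LOR difference where the wakefulness response is non-zero; that contrast needs its own paired, subject-level test.

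*Combined protocol and SAP*

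**What the plan says.** In Data Analysis, each subject's voxel time course is correlated with the mean time course of the other subjects, and these coefficients are averaged: "The inter-SC analysis will be performed on a voxel-by-voxel basis". One sentence then covers two kinds of test. It names inter-SC in each of the three states, and it says that "the difference between states (e.g. wakefulness baseline vs. LOR period) will be assessed using a phase-randomization procedure (forming a null distribution"). It does not say what is randomized, whether phases are shared across subjects or states, or what null the difference test represents. No other section names a test for the contrast.

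Anticipated Results and Implications gives the expected pattern. In wakefulness: "We expect to find a spatial hierarchy with reliable responses (inter-SC) to music starting in the primary auditory cortex". Under sedation: "We anticipate that during LOR, inter-SC in especially the frontal areas, which process long-timescale musical structures, will be reduced".

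The fMRI Protocol section adds: "Four types of music, including Jazz, Rock, Pop and Country, will be presented in a pseudo-randomized order" and "Each piece of music will be edited into 2-min duration". It does not say whether the same excerpts are played in every state.

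**The concern.** Two hypotheses share one null. Whether there is any shared response in a state is a question about zero, and destroying the shared response is the right reference. Whether inter-SC falls from wakefulness to LOR is a question about equality at whatever level the response has. Surrogates without a shared response show how much the difference varies when neither state responds. They carry no information on how far subjects differ in response strength, or on the pairing of a subject's two states.

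The contrast tests the expected loss of response under sedation, and inter-SC is how the plan quantifies music-evoked activity. A miscalibrated contrast can miss a real loss or show a false one.

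**Working it through.** **Plan's own figure.** None exists for this contrast. The N=24 in Power Analysis rests on a standardized effect of 0.56 from an earlier study and does not describe inter-SC.

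**Inputs from the documents.** 25 subjects; TR 0.8 s; 16-minute runs, so 960 / 0.8 = 1200 frames; "The first two frames of each fMRI run will be discarded", leaving 1198; high-pass filter at 0.008 Hz.

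**Assumed, because the documents give no value.** Subject i's series is x_i = a_i·s + √(1 − a_i²)·e_i, with s the shared response, e_i noise (both 1/f) and a_i the loading. Mean loading, its SD between subjects and its correlation across states were varied. True inter-SC was equal in both states; tests were two-sided at 5%.

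**Step 1: loading to inter-SC.** With alike subjects, leave-one-out inter-SC = a² / √(a² + (1 − a²)/24).
- a = 0.4: 0.16 / √0.195 = 0.36
- a = 0.3: 0.09 / √0.1279 = 0.25
- a = 0.2: 0.04 / √0.08 = 0.14
- a = 0.1: 0.01 / √0.05125 = 0.04

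**Step 2: what basic schemes do.** In the frequency domain a correlation is a sum of X_k·conj(Y_k). If every subject gets the same phase φ_k, then e^{iφ_k}·e^{−iφ_k} = 1 and every inter-SC is unchanged. The surrogate difference equals the observed one and there is no null distribution. If phases are independent by subject, or only the left-out subject is randomized, the expected inter-SC becomes zero in both states.

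**Step 3: spread.** At inter-SC 0.36 with independent phases the surrogate SD of the difference was 0.0257-0.0268 in every setting. The true SD ran from 0.0185 to 0.0506. With surrogate SD about 0.026 the critical value is 1.96 × 0.026 = 0.051, so type I error is about 2·[1 − Φ(0.051 / true SD)]:
- true SD 0.0185 (alike): ratio 2.75, about 0.6%
- true SD 0.0374 (loading SD 0.15, half shared): ratio 1.36, about 17%
- true SD 0.0506 (largest found): ratio 1.01, about 31%

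**Step 4: simulated type I error, %** (8,000 data sets per setting; Monte Carlo SE about 0.35 points at 5%). Columns: (i) phases independent by subject and state; (ii) independent by subject, reused in that subject's two states; (iii) only the left-out subject randomized; JK, the jackknife described under the fix.

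| Inter-SC | Loading SD | Cross-state correlation | i | ii | iii | JK |
|---|---|---|---|---|---|---|
| 0 | 0 | – | 5.8 | 5.3 | 15.7 | 0.9 |
| 0.04 | 0 | – | 6.6 | 6.4 | 16.1 | 1.4 |
| 0.14 | 0 | – | 5.3 | 6.1 | 11.9 | 2.8 |
| 0.14 | 0.05 | 0.5 | 8.2 | 8.2 | 15.4 | 3.3 |
| 0.25 | 0 | – | 2.6 | 2.9 | 5.8 | 3.5 |
| 0.36 | 0 | – | 0.8 | 1.3 | 1.7 | 4.1 |
| 0.36 | 0.10 | 0.8 | 2.6 | 3.3 | 4.4 | 4.3 |
| 0.36 | 0.10 | 0.5 | 7.4 | 9.2 | 11.4 | 4.7 |
| 0.36 | 0.15 | 0.5 | 17.0 | 19.2 | 23.4 | 4.8 |
| 0.36 | 0.15 | 0 | 29.5 | 32.7 | 35.9 | 5.1 |

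**Step 5: robustness.** Smaller repeats of scheme (i) at inter-SC 0.36 gave 0.5% and 0.8% with alike subjects, and 17.1% and 14.4% at loading SD 0.15, half shared. The plan censors motion frames ("output data included zero values at censored time points"); with 10% of frames zeroed the same two settings gave 1.1% and 18.1%. With a different noise model (AR(1), coefficient 0.85; 604 data sets per setting) and inter-SC 0.27, scheme (i) gave 2.0% with alike subjects and 28.6% when response amplitude varied by subject and state with a coefficient of variation of 0.5.

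**The case against.** The strongest reply is that the plan contains none of these schemes. It names a procedure without describing it and cites a source for inter-SC that cannot be consulted here. A variant built for the difference may be intended. That stands: the text underspecifies the contrast and does not prove that a wrong test will be run. It does not remove the point, because no such variant is described.

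Second, schemes (i) and (ii) do impose equal inter-SC, at zero, and are near nominal at weak inter-SC with alike subjects (5.3-6.6%). That also stands. The problem arises where the response is non-zero, and grows with its strength and with variation between subjects. A reader might infer that the test is simply too strict when subjects are alike. Scheme (iii) contradicts that, at 11.9-16.1% for inter-SC of 0.14 or below.

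Third, the large figures need large assumed heterogeneity. With loading SD 0.10 and cross-state correlation 0.8, scheme (i) gives 2.6%. A reader might infer from the upper rows of the range that the trial will report false loss of response. The documents give no inter-SC level, spread or cross-state correlation, so they do not support that inference, nor the opposite one that real loss will be missed.

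Fourth, a replacement can cost power where the response is weak, which may include the frontal areas of interest. This stands and bears on the choice of test.

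**Conclusion.** The point holds in limited form. As written, the phase-randomization null is not matched to the wake-versus-LOR difference wherever wakefulness inter-SC is non-zero, which the plan itself expects. Under the assumed model at inter-SC about 0.36, type I error for independent phases ranges from about 1% with alike subjects to about 14-17% with loading SD 0.15 half shared across states, and to about 30% in the extreme case of independent variation. The direction and size in this trial cannot be derived from the documents.

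A reader might also infer that the within-state maps, including the LOR map, are invalid. They are not challenged: a null of no shared response is the right one for them.

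This should be settled before analysis. The contrast carries a main expectation of the study, and correcting it needs no new data.

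**What to change.** Keep phase randomization, with phases independent per subject, for the within-state maps. For differences between states, write a separate test:

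- Include subjects with usable music runs in both states. The statistic at each voxel is mean leave-one-out inter-SC in wakefulness minus that in LOR, recomputed at every step below.
- State whether the same excerpts are played in both states. If they are, and runs are aligned by excerpt, swap whole wake and LOR time courses at random within subjects to form the null. Type I error was 4.3-5.1% in the AR(1) runs and about 4-8% in a smaller check.
- Otherwise delete each subject in turn, and refer the difference divided by its jackknife standard error to t with n − 1 degrees of freedom. Type I error was about 3.5-6% at inter-SC 0.36 across all runs.
- Do not apply a plain paired t test to the leave-one-out values. They are mutually dependent, and its type I error was about 9-19%.

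If phase randomization is kept for the contrast instead, the plan must describe the variant and state its null.

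**Cost.** Analysis wording and light computing; no design change. The jackknife is conservative at weak inter-SC (about 3% type I error at 0.14, about 1% at zero). For a drop from 0.14 to 0.04, unadjusted power was about 89%, against 94% for the swap and 97% for independent phases; part of that last gap is the inflated error of phase randomization (8.2% in that setting at 0.14). At strong inter-SC with alike subjects the order reverses: for 0.36 to 0.31, 78% for the jackknife against 62% for independent phases. The swap tests full exchangeability of the two states, so it may also respond to a change other than in inter-SC. If excerpts differ between states, any test of the difference also carries an excerpt effect. This change does not address multiplicity across voxels or any further dropping of frames.
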